**Table 2 Disease Control Rate – Third Line** 

	Monotherapy (Historical)	Combination * (Historical)	Combination with BBI608 (Expected)
Cetuximab	30-40% 	~ 63% 	60% or more
Panitumumab	30-40% 	~ 68% 	60% or more
Capecitabine	~ 15% 	~ 45% 	60% or more

\* Cetuximab + Irinotecan
Panitumumab + Irinotecan
Capecitabine + Mitomycin C

For the Cetuximab and Panitumumab combination cohorts, if the disease control rate in stage 1 reaches 3 of 8 or above, additional patients will be enrolled into the stage 2 cohort. For the

Capecitabine combination cohort, if the disease control rate in stage 1 reaches 2 of 6 or above, additional patients will be enrolled into the stage 2 cohort.

To evaluate the tolerability of BBI608, patients from each arm will be assigned to one of 4 subcohorts (with 6 patients in each sub-cohort IA, IB, IIA, IIB). The evaluation of tolerability will be done at select centers for the study arm that is continuing patient accrual and in which a total of 50 evaluable patients has not been reached. For each combination arm, patients assigned to sub-cohorts IA and IB will receive BBI608 at 240 mg po twice daily (480 mg total daily dose) starting on day 1 of cycle 1. Intra-patient dose escalation of BBI608 to 480 mg po twice daily (960 mg total daily dose) is allowed as tolerated. Patients assigned to sub-cohorts IIA and IIB will receive BBI608 at 480 mg po twice daily (960 mg total daily dose) starting on day 1 of cycle 1. In case of toxicity, dose adjustment of BBI608 is permitted, as recommended in dose modification guidelines. Additionally, patients assigned to sub-cohorts IA and IIA will receive prophylactic anti-diarrheal treatment starting the day prior to day 1 of cycle 1. Patients assigned to sub-cohorts IB and IIB will anti-diarrheal treatment on an as needed basis starting with development of diarrhea above baseline. For each combination regimen, patients will be sequentially assigned to each of the 4 sub-cohorts in the following order until 6 patients are accrued on each of the sub-cohorts: IA, IB, IIA, and IIB. If required, up to additional 20 patients may be assigned to selected sub-cohorts to validate the observations in initial 6 patients.

Table 3 Tolerability Analysis of BBI6	U8
---------------------------------------	----

Sub-cohort	BBI608 Starting Dose Level	Anti-diarrheal Administration
IA	240 mg bid (480 total daily dose) 	Prophylactic
IB	240 mg bid (480 total daily dose) 	As needed
IIA	480 mg bid (960 total daily dose) 	Prophylactic
IIB	480 mg bid (960 total daily dose) 	As needed

Intra-patient dose escalation of BBI608 to 480 mg po twice daily (960 mg total daily dose) is allowed as tolerated.

## 4.2 Rationale for Study Design

Considerable data has been collected from the Phase I monotherapy study of BBI608 (Protocol BBI608-101) conducted in advanced oncology patients who have failed multiple previous regimens. Dose escalation for BBI608 has been successfully conducted from a total daily dose of 20 mg to 2000 mg total daily dose. Further dose escalation is limited by pill burden. A MTD was not reached. In addition, a phase Ib/II trial of BBI608 in combination with paclitaxel in patients with advanced malignancies carried out under IND 100,887 has shown that BBI608 given at 500 mg bid (1000 mg total daily dose) in combination with weekly paclitaxel is well tolerated.

Combination of cancer stem cell therapeutics with chemotherapy or a targeted agent would allow simultaneous inhibition of cancer stem cells as well as non-stem regular cancer cells.

Based on the activity seen in colorectal cancer patients in the phase I monotherapy trial, and the excellent safety profile of BBI608, combination of BBI608 with Cetuximab, or Panitumumab or Capecitabine provides a good option for these patients.

### 4.3 Selection of Dose

<sup>2In case of toxicity, dose adjustment of BBI608 is permitted.

The dose escalation of BBI608 in the BBI608-101 Phase I study has reached a total daily dose of 2000 mg without dose-limiting toxicity. No MTD was reached and further dose escalation above 2000 mg total daily dose was limited by pill burden. Adverse events observed in the BBI608-101 phase I trial have been generally mild with the most common being: diarrhea, nausea, and fatigue. Grade 3 events include: fatigue or transient diarrhea. No bone marrow suppression or neuropathy was observed.

In the BBI608-224 study, administration of BBI608 will be begin at a dose of 480 mg twice daily with a total daily dose of 960 mg, in combination with Cetuximab, or Panitumumab, or Capecitabine with exception of patients enrolled into the IA and IB combination arm sub-cohorts, for whom administration of BBI608 will begin at a dose of 240 mg twice daily with a total daily dose of 480 mg in cycle 1. Intra-patient dose escalation of BBI608 to 480 mg po twice daily (960 mg total daily dose) is allowed as tolerated.

## •

## 4.4 Risk Benefit Assessment

Cancer stem cell inhibitors offer an exciting approach to the treatment of advanced malignancies. Preclinical studies of BBI608 indicate that the drug is active against a wide range of solid tumors. Encouraging signs of antitumor activity have been observed in the BBI608-101 phase I trial.

Combination of cancer stem cell therapeutics with chemotherapy or targeted agents would allow enhanced simultaneous inhibition of cancer stem cells as well as non-stem regular cancer cells.

BBI608 has been well tolerated in phase I trials. A MTD was not reached in the BBI608-101 Phase I study with doses escalated from 20 mg up to 1000 mg bid (2000 mg total daily dose). Further dose escalation above 2000 mg/day was limited by pill burden.

Adverse events observed in the BBI608-101 phase I trial have been generally mild with the most common being: diarrhea, nausea, and fatigue. Grade 3 events include: fatigue or transient diarrhea. There is no clinically significant overlap between adverse events observed for BBI608 and the adverse effects of Cetuximab, Panitumumab, or Capecitabine.

The sponsor believes that the proposed study is acceptable in the context of its risks and benefits.

# 4.5 Dose-Limiting Toxicity

Dose-limiting toxicity is defined by the occurrence of any of the following toxicities possibly or probably related to BBI608 in combination with Cetuximab, or Panitumumab or Capecitabine within 28 days of treatment. DLT will be scored during the 28 days of BBI608 treatment.

- Grade 4 hematological toxicity
- Grade 3 or 4 non-hematological toxicity, except:
  - o Grade 3 or 4 nausea/vomiting/anorexia, diarrhea and fatigue will be considered a DLT only if it persists more than three (3) days despite optimal medical management
  - o Alopecia will not be considered a DLT

Adverse events considered related to Cetuximab, or Panitumumab or Capecitabine will not be considered DLTs.

## 4.6 Study Duration

Patients will receive treatment with BBI608 and Cetuximab, or Panitumumab, or Capecitabine until progression of disease, unacceptable toxicity or another of the discontinuation criteria is documented (see Section 5.6). It is expected that most patients will receive between one and four cycles of BBI608 and Cetuximab, or Panitumumab, or Capecitabine for a treatment period of 4 to 16 weeks.

#### 5 STUDY VISITS

Study Visits will consist of a Pre-Study Evaluation, during which the patient is evaluated to determine suitability for entry into the study, Cycle 1 Evaluations which will be performed on Weeks 1, 2, 3 and 4 of the first cycle only for Cetuximab, on Weeks 2 and 4 the first cycle only for Panitumumab, and on Weeks 2 and 3 the first cycle only for Capecitabine, evaluations in Cycle 2 and beyond, which will be performed in Week 1 or 2 of each cycle, and an End-of-Study Evaluation. (See Section 14 for a schedule of Assessments)

Following the Pre-Study Evaluation and a determination by a Principal Investigator that the patient meets all inclusion/exclusion criteria and signs the informed consent, the patient will be considered entered into the study.

## 5.1 Informed Consent

Patients who agree to participate will sign the approved informed consent and will be provided a copy of the signed document.

## 5.2 Pre-Study Evaluations (Baseline) (1 week ±3 days prior to the first dose of BBI608\*)

After written informed consent is obtained according to ICH-GCP and local regulations, the patient will be evaluated for inclusion and exclusion criteria according to the eligibility criteria listed in Section 3.

The following will be evaluated and documented within seven days prior to first dose of BBI608:

- Medical history
- Physical examination

- Karnofsky performance status (see Section 15)
- Vital signs (weight, temperature, blood pressure, height, respiration and pulse)
- Hematology (see Section 6.3)
- Blood chemistry (see Section 6.3)
- Liver function tests (see Section 6.3)
- Electrolytes (see Section 6.3)
- Urinalysis (see Section 6.3)
- Serum pregnancy test (if applicable)
- Tumor markers if applicable
- Tumor biopsy, if applicable (see Section 6.5.1)
- 12-lead electrocardiogram (ECG)
- Tumor measurement and staging[computed tomography (CT) or magnetic resonance imaging (MRI) acceptable] \*

\*All CT and MRI scans can be used as the baseline assessment if they were performed within three weeks prior to the first scheduled dose of BBI608.

Archival tissue samples from a prior biopsy or surgery should be collected from all patients enrolled in the clinical trial if they are available (See Section 17: Appendix E).

## 5.3 On-Study Assessments

## 5.3.1 Cetuximab Arm

## 5.3.1.1 Week 1 (Cycle 1, Day 1)

- Dispense BBI608 (four day supply)
- 12-lead electrocardiogram (2 hours after first BBI608 dose)

## 5.3.1.2 Week 1 (Cycle 1, Day 5)

- Karnofsky performance status
- Vital signs (weight, pulse)
- Hematology (see Section 6.3)
- Blood chemistry (see Section 6.3)
- Liver function tests (see Section 6.3)
- Electrolytes (see Section 6.3)
- Urinalysis (see Section 6.3)
- Assess AEs
- Record concomitant medication
- Cetuximab, IV infusion starting about 3 hours after morning dose of BBI608
- The second dose of BBI608 will be given approximately 12 hours after the first dose.
- Blood samples for pharmacokinetics, (for only the first 6 patients enrolled in this arm).
- Dispense BBI608 (one week supply)

Blood samples for pharmacokinetics will be collected immediately prior to the first dose of BBI608 and will continue through 171 hours after administration of the first dose of BBI608. Specific details for the collection of blood samples for pharmacokinetics can be located in Sections 6.4 and Section 16.

# 5.3.1.3 Week 2 (Cycle 1, Day 8)

• Tumor biopsy, if applicable (see Section 6.5.1)

## 5.3.1.4 Week 2 (Cycle 1, Day 12)

The following assessments will be made during this visit:

- Karnofsky performance status
- Vital signs (weight, pulse)
- Hematology (see Section 6.3)
- Blood chemistry (see Section 6.3)
- Liver function tests (see Section 6.3)
- Electrolytes (see Section 6.3)
- Assess AEs
- Record concomitant medication
- Cetuximab IV infusion, starting at about 3 hours after morning dose of BBI608 Dispense BBI608 (one week supply)

## 5.3.1.5 Week 3 (Cycle 1, Day 19)

The following assessments will be made during this visit:

- Karnofsky performance status
- Vital signs (weight, pulse)
- Hematology (see Section 6.3)
- Blood chemistry (see Section 6.3)
- Liver function tests (see Section 6.3)
- Electrolytes (see Section 6.3)
- Urinalysis (see Section 6.3)
- Assess AEs
- Record concomitant medication
- Cetuximab IV infusion, starting at about 3 hours after morning dose of BBI608
- Dispense BBI608 (one week supply)

## 5.3.1.6 Week 4 (Cycle 1, Day 26)

The following assessments will be made during this visit:

- Karnofsky performance status
- Vital signs (weight, pulse)
- Hematology (see Section 6.3)
- Blood chemistry (see Section 6.3)
- Liver function tests (see Section 6.3)
- Electrolytes (see Section 6.3)
- Urinalysis (see Section 6.3)
- Assess AEs
- Record concomitant medication
- Cetuximab IV infusion, starting at about 3 hours after morning dose of BBI608
- Blood samples for pharmacokinetics, (for only the first six patients enrolled in this arm.)
- The second dose of BBI608 will be given about approximately 12 hours after the first dose.
- Dispense BBI608 (one week supply)

Blood samples for pharmacokinetics will be collected immediately prior to the first dose of BBI608 and will continue through 171 hours after administration of the first dose of BBI608. Specific details for the collection of blood samples for pharmacokinetics can be located in Sections 6.4 and Section 16.

## 5.3.2 Panitumumab Arm

# 5.3.2.1 Week 1 (Cycle 1, Day 1)

- Dispense BBI608 (1 week supply)
- 12-lead electrocardiogram (2 hours after first BBI608 dose)

## 5.3.2.2 Week 2 (Cycle 1, Day 8)

- Karnofsky performance status
- Vital signs (weight, pulse)
- Hematology (see Section 6.3)
- Blood chemistry (see Section 6.3)
- Liver function tests (see Section 6.3)
- Electrolytes (see Section 6.3)
- Urinalysis (see Section 6.3)
- Assess AEs
- Tumor biopsy, if applicable (see Section 6.5.1)
- Record concomitant medication
- Panitumumab, IV infusion starting about 3 hours after morning dose of BBI608
- The second dose of BBI608 will be given approximately 12 hours after the first dose.
- Blood samples for pharmacokinetics, (for only the first six patients enrolled in this arm.)
- Dispense BBI608 (two week supply)

Blood samples for pharmacokinetics will be collected immediately prior to the first dose of BBI608 and will continue through 171 hours after administration of the first dose of BBI608. Specific details for the collection of blood samples for pharmacokinetics can be located in Sections 6.4 and Section 16.

# 5.3.2.3 Week 4 (Cycle 1, Day 22)

The following assessments will be made during this visit:

- Karnofsky performance status
- Vital signs (weight, pulse)
- Hematology (see Section 6.3)
- Blood chemistry (see Section 6.3)
- Liver function tests (see Section 6.3)
- Electrolytes (see Section 6.3)
- Urinalysis (see Section 6.3)
- Assess AEs
- Record concomitant medication
- Panitumumab IV infusion, starting at about 3 hours after morning dose of BBI608
- The second dose of BBI608 will be given approximately 12 hours after the first dose.

- Blood samples for pharmacokinetics, (for only the first six patients enrolled in this arm.)
- Dispense BBI608 (two week supply)

Blood samples for pharmacokinetics will be collected immediately prior to the first dose of BBI608 and will continue through 171 hours after administration of the first dose of BBI608. Specific details for the collection of blood samples for pharmacokinetics can be located in Sections 6.4 and Section 16.

## 5.3.3 Capecitabine Arm

## 5.3.3.1 Week 1 (Cycle 1, Day 1)

- Dispense BBI608 (one week supply)
- 12-lead electrocardiogram (2 hours after first BBI608 dose)

# 5.3.3.2 Week 2 (Cycle 1, Day 8)

- Karnofsky performance status
- Vital signs (weight, pulse)
- Hematology (see Section 6.3)
- Blood chemistry (see Section 6.3)
- Liver function tests (see Section 6.3)
- Electrolytes (see Section 6.3)
- Urinalysis (see Section 6.3)
- Assess AEs
- Tumor biopsy, if applicable (see Section 6.5.1)
- Record concomitant medication
- The second dose of BBI608 will be given approximately 12 hours after the first dose.
- Blood samples for pharmacokinetics, (for only the first six patients enrolled in this arm.)
- Dispense BBI608 (one week supply)
- Dispense Capecitabine (two week supply)

Blood samples for pharmacokinetics will be collected immediately prior to the first dose of BBI608 and will continue through 24 hours after administration of the first dose of BBI608. Specific details for the collection of blood samples for pharmacokinetics can be located in Sections 6.4 and Section 16.

## 5.3.3.3 Week 3 (Cycle 1, Day 15)

The following assessments will be made during this visit:

- Karnofsky performance status
- Vital signs (weight, pulse)
- Hematology (see Section 6.3)
- Blood chemistry (see Section 6.3)
- Liver function tests (see Section 6.3)
- Electrolytes (see Section 6.3)
- Urinalysis (see Section 6.3)
- Assess AEs
- Record concomitant medication

• Dispense BBI608 (1 week supply)

# 5.3.3.4 Week 4 (Cycle 1, Day 21)

The following assessments will be made during this visit:

- Karnofsky performance status
- Vital signs (weight, pulse)
- Hematology (see Section 6.3)
- Blood chemistry (see Section 6.3)
- Liver function tests (see Section 6.3)
- Electrolytes (see Section 6.3)
- Urinalysis (see Section 6.3)
- Assess AEs
- Record concomitant medication
- The second dose of BBI608 will be given approximately 12 hours after the first dose.
- Blood samples for pharmacokinetics, (for only the first six patients enrolled in this arm.)
- Dispense BBI608 (1 week supply)

Blood samples for pharmacokinetics will be collected immediately prior to the first dose of BBI608 and will continue through 24 hours after administration of the first dose of BBI608. Specific details for the collection of blood samples for pharmacokinetics can be located in Sections 6.4 and Section 16.

## 5.3.3.5 Monthly Evaluations (Cycle 2 and beyond, all arms)

## 5.3.3.6 Week 1 or 2 (Day 1 – Capecitabine: Day 5 – Cetuximab; Day 8 - Panitumumab)

Patients will have the following assessments:

- Physical examination
- Karnofsky performance status
- Vital signs (weight, temperature, blood pressure, respiration and pulse)
- Hematology (see Section 6.3)
- Blood chemistry (see Section 6.3)
- Liver function tests (see Section 6.3)
- Electrolytes (see Section 6.3)
- Urinalysis (see Section 6.3)
- Tumor markers, if applicable
- Assess adverse events (AE)
- Record concomitant medication
- Cetuximab or Panitumumab IV infusion starting about 3 hours after morning dose of BBI608 (for Cetuximab and Panitumumab arms respectively)
- Dispense BBI608 (28 day supply)
- Dispense Capecitabine (sufficient for Cycle)

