### 4 INVESTIGATIONAL PLAN

# 4.1 Overall Study Design

This is an open-label, multicenter Phase II study of oral BBI608 administered with Cetuximab, or Panitumumab, or Capecitabine to patients with advanced metastatic colorectal cancer. The study is based on a Simon 2-stage design that will examine the safety, tolerability and pharmacokinetics of BBI608 and Cetuximab, or Panitumumab, or Capecitabine, and assess the preliminary anti-tumor activity of BBI608 when administered in combination with Cetuximab, or Panitumumab, or Capecitabine in patients with advanced colorectal cancer.

BBI608 treatment will be at a dose level of 480 mg twice daily (960 mg total daily dose). In each cycle, BBI608 will be taken daily continuously for 4 weeks (28 days). BBI608 will be administered twice daily approximately one hour prior to or two hours after meals with the first dose given in the morning and approximately 12 hours between doses.

For patients receiving Cetuximab therapy, Cetuximab will be administered IV on day 5 of cycle 1 at 400 mg/m² intravenous infusion over 120 minutes as the initial dose, then weekly at 250mg/m² over 60-minutes at subsequent cycles.

For patients receiving Panitumumab therapy, Panitumumab will be administered IV on day 8, and 22 of each 28 day cycle at 6 mg/kg over 60 minutes.

For patients receiving Capecitabine therapy, Capecitabine will be administered orally at 1000 mg/m^2 bid daily on days 8-21 every three weeks.

Cycles will be repeated until progression of disease, unacceptable toxicity, or another discontinuation criterion is met. In the case of toxicity, adjustment is permitted. If administration of Cetuximab, or Panitumumab, or Capecitabine is discontinued due to Cetuximab, or Panitumumab, or Capecitabine-related toxicity, administration of BBI608 will be continued until disease progression if tolerated.

Initially, 6 patients will be enrolled in each combination arm at a dose level of 480 mg twice daily (960 mg total daily dose) BBI608. If  $\leq 1$  out of 6 patients has an observable DLT in the combination regimen, then that arm of the study will continue to enroll patients at 480 mg po twice daily (960 mg total daily dose) of BBI608 following the Simon 2-stage design (see Table 1). If

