## 7.1.3 Cetuximab, Panitumumab, or Capecitabine Administration

- Detailed instructions for the preparation, premedication, and administration of Cetuximab, Panitumumab, or Capecitabine are provided in the Product Labels approved by Health Canada or US FDA.
- Cetuximab will be administered via IV on Days 5, 12, 19 and 26 of a 28 day cycle, about 3 hours after the first daily dose of BBI608. Panitumumab will be administered via IV on Days 8, and 22 of a 28 day cycle, about 3 hours after the first daily dose of BBI608. Capecitabine will be administered orally twice-daily for two weeks out of three weeks. The first dose of Capecitabine should be taken about 3 hours after the first daily dose of BBI608 on day 8 of each 3 week cycle of Capecitabine.

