## 7.2.3 Capecitabine

## Hematological:

ANC (x10  /L)		Platelets (x10  /L)	1st Event Dose	2nd Event Dose	3rd Event Dose	4th Event Dose
≥ 1.5	and	≥ 75	100%	100%	100%	100%
1-1.49	or	50-74.9	delay* then 100%	delay* then 75%	delay* then 50%	discontinue
0.5 - 099	or	25 - 49.9	delay* then 75%	delay* then 50%	discontinue	discontinue
< 0.5	or	< 25	discontinue or delay* then 50%	discontinue	discontinue	discontinue

\* delay until ANC ≥ 1.5x10^9/L and platelets ≥ 75 x10^9/L

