### BBI608 + Capecitabine

End of Study Visit			≤30 days from last BBI608 dose			X		X	×	X	X	X	X	X	X	X	X		$\mathbf{X}^7$	X	X		
	pı	4	21																				
	z Beyor	3	15	± 1 day																			
1S1	Cycle 2 & Beyond	2	80	± 1																			
ıluatior	Ċ	1	1			×		×	×	X	X	X	X	X		X				X	X	X	×
Study Evaluations		4	21					×	×	X	X	X	X	X				X		X	X	X	
Stı	le 1	3	15	day				×	×	X	X	X	X	X						X	X	X	
	Cycle 1	2	∞	± 1 day				×	×	X	X	X	X	X			X	X		X	X	X	X
		1	1												X							X	
Pre-Study	Evaluation	0	0	-7 ± 3 days	X	X	X	X	×	X	X	X	X	X	X	X	X		$X^6$	X			
Tests & Procedures		Week	Day	Window	Medical history	Physical examination	Serum pregnancy test 	Karnofsky performance status	Vital signs, Weight	Hematology 	Blood chemistry 	Liver function tests 	Electrolytes 	Urinalysis 	12-Lead electrocardiogram	Tumor markers 	Tumor biopsy 	Pharmacokinetics (first six patients only)	Tumor measurement & staging 4,5	Concomitant medications	Adverse events 	Dispense BBI608	Dispense Capecitabine

Confidential

Calculated from the date of first BBI608 dose. Refer to Section 6.3 for description of laboratory assessments.

Ifapplicable

Including tumor measurements, following RECIST 1.1.

Prior to cycle 3 and every other cycle thereafter, assessments must be made utilizing the same imaging method as baseline Unless CT/MRI has been performed within last three weeks.

.1. .2. .3. .2. .7. .8. .9. .7. .8. 

Unless CT/MRI has been performed within last four weeks.

Patients will be followed until resolution of any drug-related AE or SAE occurring during the study or within 30 days of last BBI608 administration.

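### Arm C gives capecitabine on a 21-day calendar but schedules assessments and dispensing on a 28-day one, so from cycle 2 some courses start without scheduled counts or toxicity grading, and the capecitabine dose denominator per cycle is not fixed

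*Protocol*

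**What the plan says.** **Dosing.** Protocol 4.1 and the synopsis give capecitabine "bid daily on days 8-21 every three weeks". Protocol 7.1.3 repeats the pattern ("Capecitabine will be administered orally twice-daily for two weeks out of three weeks") and places the first dose of a course "on day 8 of each 3 week cycle of Capecitabine". Capecitabine therefore has its own 21-day cycle.

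**Study cycle.** Protocol 4.1 sets the study cycle by BBI608: "In each cycle, BBI608 will be taken daily continuously for 4 weeks (28 days"). SAP 2.1 also uses 28 days.

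**Visits and supply.** Protocol 5 describes "evaluations in Cycle 2 and beyond, which will be performed in Week 1 or 2 of each cycle". Protocol 5.3.3.6 fixes that visit at Day 1 for the capecitabine arm. It carries hematology, chemistry, liver tests, adverse event assessment and the instruction "Dispense Capecitabine (sufficient for Cycle"). The Arm C table in Appendix A prints Day 8, 15 and 21 columns for cycle 2 and beyond, but marks assessments and dispensing under Day 1 only.

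**Dose rules.** The tables in Protocol 7.2.3 set full dose, delay, reduction or discontinuation from neutrophils, platelets and toxicity grade, for example "delay until ANC ≥ 1.5x10".

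**Analysis.** Protocol 7.3 and SAP 8.2.1 define capecitabine compliance as amount taken over amount planned. SAP 8.2.1 derives the planned dose intensity from the dose intended in a cycle and the cycle's length. Protocol 10.4 requires 80% of one complete cycle of BBI608 and a combination drug for the primary efficacy population.

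**The concern.** A 21-day drug calendar and a 28-day visit calendar drift apart. In cycle 1 this does no harm: Arm C has visits on days 8, 15 and 21, and the second course falls on the cycle 2 Day 1 visit. After that, course starts move away from the only scheduled visit, while the dose tables still need current counts and grades.

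Two things are at stake. The first is safety. Followed exactly as written, a patient can finish one course and begin the next with no scheduled count or toxicity grading in between. The second is measurement. If a cycle means 28 days, the planned capecitabine dose changes from cycle to cycle, so compliance and by-cycle dose intensity depend on a choice that the documents do not state.

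**Working it through.** The plan gives no figure of its own here, so the check is a calendar enumeration.

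**Inputs.** Course starts: 8 + 21k (Protocol 4.1, 7.1.3). Arm C visits with assessments: days 8, 15 and 21 in cycle 1, then 1 + 28m (Protocol 5.3.3, Appendix A). Window: ±1 day (Appendix A). Expected treatment: one to four cycles (Protocol 4.6). Assumption: no interruptions or delays.

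**Realignment.** The least common multiple of 21 and 28 is 84 days.

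| Course start | Cycle and day | Last scheduled counts | Age of counts |
|---|---|---|---|
| 29 | C2 D1 | day 29 | 0 days |
| 50 | C2 D22 | day 29 | 21 days |
| 71 | C3 D15 | day 57 | 14 days |
| 92 | C4 D8 | day 85 | 7 days |
| 113 | C5 D1 | day 113 | 0 days |

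The pattern then repeats. An uncovered start is never closer than 7 days to a visit. Applying ±1 day to both dates closes at most 2 days, so the window changes nothing.

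The three uncovered starts differ in weight:
- **Day 50:** the last scheduled counts date from day 29, when the previous course (days 29–42) began. Nothing is scheduled during or after that course.
- **Day 71:** the last counts (day 57) fall inside the previous course (days 50–63).
- **Day 92:** the last counts (day 85) come one day after the previous course (days 71–84). This is the mildest case.

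**Share of starts after cycle 1 with no scheduled assessment**

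| Treated through | Uncovered / starts |
|---|---|
| Cycle 2 | 1 of 2 |
| Cycle 3 | 2 of 3 |
| Cycle 4 | 3 of 4 |

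A patient treated for one cycle only has none.

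**Capecitabine days per 28-day cycle**
- Cycle 1 (days 1–28): days 8–21 = 14
- Cycle 2 (days 29–56): days 29–42 and 50–56 = 14 + 7 = 21
- Cycle 3 (days 57–84): days 57–63 and 71–84 = 7 + 14 = 21
- Cycle 4 (days 85–112): days 92–105 = 14

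Over days 29–112 the 3-week calendar needs 21 + 21 + 14 = 56 dosing days. If the supply instruction meant one 14-day course per Day 1 visit, three visits would supply 42 days, which is (56 − 42)/56 = 25% less. The wording does not say which cycle is meant.

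**Effect on dose intensity.** The daily dose in the protocol is 2 × 1000 = 2000 mg/m². The 3-week regimen intends 14 × 2000 / 3 weeks = 9333 mg/m² per week. For a fully adherent patient, the amount per week in a 28-day cycle is:
- 14-day cycles: 14 × 2000 / 4 = 7000, or 75% of 9333
- 21-day cycles: 21 × 2000 / 4 = 10,500, or 112.5% of 9333

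Perfect adherence would therefore read as 75% or 112.5% by 28-day cycle, and as 100% by 21-day cycle.

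**Effect on the 80% rule.** Fourteen capecitabine days in cycle 2 are 14/21 = 67% on the 3-week calendar, and 14/14 = 100% if one course per 28-day cycle is intended. In cycle 1 both readings give 14 planned days, so the rule is unaffected there.

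**The case against.** The strongest reply is that nothing here is impossible to follow. No section demands counts on the first day of a course. The 7.2.3 tables respond to events, a schedule of assessments does not bar extra tests, and SAP 8.2.4.2 provides for unscheduled laboratory results. Protocol 8.1.1 makes the investigator responsible for safety monitoring. Protocol 7.1 and 7.1.3 also refer to product labels, which cannot be checked from the documents. This stands: a reader might infer that a site cannot comply with dosing, schedule and dose tables together, but the documents do not support that. They show only that the scheduled visits alone do not supply the tables' inputs.

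A second reply is that monthly evaluation is a deliberate choice for all arms, since Arms A and B also receive infusions between assessment visits. That is fair as to frequency. However, their infusions share the 28-day calendar and bring the patient to the site. Arm C's oral courses drift against it.

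A third reply is that a 3-week regimen has a constant planned weekly dose, and that SAP 8.2.1 lets exposure summaries depend on how a drug is dosed. This stands for intensity over the whole treatment period. It does not settle by-cycle summaries, because the SAP defines the study cycle as 28 days and names no separate capecitabine cycle.

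Two more inferences go too far. One is that sites will split between 3-week and 4-week dosing; the dosing text says three weeks throughout, and nothing shows such a split. The other is that three of four starts are uncovered for every patient, which requires uninterrupted dosing into cycle 4.

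**Conclusion.** The mismatch is real and follows from the protocol's own calendars. From cycle 2, the course starts on days 50, 71 and 92 have no scheduled assessment, with last scheduled counts 21, 14 and 7 days old. The affected share after cycle 1 is 1 of 2, 2 of 3 or 3 of 4 for treatment through cycle 2, 3 or 4. Dose delays would shift the dates and the shares.

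This is more than missing detail. Dose rules lack scheduled inputs at the day 50 and day 71 starts and have week-old inputs at day 92, and planned capecitabine days per 28-day cycle alternate between 14 and 21. It is not proof that the protocol cannot be followed. Reading the regimen as days 8–21 of each 28-day cycle would remove the drift, but it contradicts the three-week wording in 4.1 and 7.1.3, and every start would still fall 7 days after the visit.

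**What to change.** Reconcile the synopsis and Protocol 4.1, 5.3.3.6, 7.1.3, 7.2.3 and the Arm C table in Appendix A, so that capecitabine dosing, scheduled assessments, dispensing and the dose tables all refer to one stated calendar. Say which cycle the supply instruction means. Which calendar and which monitoring rule apply is for the sponsor to decide.

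Then base the capecitabine denominators on that calendar: compliance in Protocol 7.3, the 80% rule in Protocol 10.4, and the intended dose, dose intensity and compliance in SAP 8.2.1. The SAP should state the cycle length used for by-cycle capecitabine summaries.

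The cost is a protocol amendment and a short SAP clarification, with no new type of test. If the 3-week calendar is kept and visits follow it, Arm C has 84/21 = 4 visits per 84 days instead of 84/28 = 3, which is one more. If Arm C dosing has already ended, only the analysis definitions remain to be settled.
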